5.8.1 Procedures for discontinuation of a subject from investigational product

A subject that discontinues will always be asked about the reason(s) for discontinuation and the presence of any adverse events. The Principal Investigator/sub-investigator will perform the best possible observation(s), test(s) and evaluation(s) as well as give appropriate medication and all possible measures for the safety of the subject. Adverse events will be followed up and study drug should be returned by the subject.

Withdrawal from the study

On patient withdrawal of consent, the assessments required at Study Completion (Visit 4, see Table 2) should be performed where possible. Patient data will not be collected beyond the date of consent withdrawal.

Patients who withdraw their consent for study participation will no longer receive any protocol-mandated assessments (including assessments for the PK subgroup for those patients also enrolled in this subgroup).

Withdrawal from the PK subgroup

Patients who withdraw from the PK subgroup will not undergo further protocol-mandated assessments specific to the PK subgroup beyond the point of withdrawal. Patients who withdraw their consent for participation in the PK subgroup should be asked whether they also wish to withdraw their consent to participate in the main study. In this case, the above procedures should be followed for discontinuation from the study.

5.9 Withdrawal from study

Subjects are at any time free to withdraw from study (investigational product and assessments), without prejudice to further treatment (withdrawal of consent). Such subjects will always be asked about the reason(s) and the presence of any adverse events. If possible, they will be seen and assessed by an investigator. Adverse events will be followed up (See Sections 6.4.3 and 6.4.4); and study drug should be returned by the subject.

6. COLLECTION OF STUDY VARIABLES

6.1 Recording of data

The Rave Web Based Data Capture (WBDC) system will be used for data collection and query handling.

The Principal Investigator/sub-investigator will record data on the observations, tests and assessments specified in the protocol on the electronic CRFs (eCRFs) provided by AstraZeneca. The eCRF will be accompanied with 'Instructions for the Investigator', which should be followed. These instructions provide guidance for the recording of study data in the eCRF including how to change data incorrectly recorded.

The investigator(s) will ensure that data are recorded on the eCRF as specified in the study protocol and in accordance with the instructions provided.

The investigator(s) ensures the accuracy, completeness, and timeliness of the data recorded and of the provision of answers to data queries according to the Clinical Study Agreement with applicable information. The principal investigator will sign the completed eCRF. A copy of the completed eCRF will be archived at the study site.

6.2 Data collection and enrolment

6.2.1 Screening and demographic measurements

The following screening and demographic data will be collected in the eCRF (see Table 2 for the timing of these assessments). Tests performed before screening may be used as screening assessments with patient informed consent

- Provision of written informed consent
 - Provision of written informed consent must be obtained prior to screening for all patients.
- Date of birth, sex, and race
- Relevant medical and surgical history, including menstrual status and concurrent illness
- Urine pregnancy test
- Previous therapy, including surgery for early breast cancer (concomitant medications will be recorded from the informed consent day until the Study Completion Visit)
- Physical examination
- Bone scan and chest assessment
 - If there are any hotspots detected by bone scan, then they should be evaluated as appropriate according to local practice (eg, by x ray, computed tomography scan, or MRI).
 - Chest assessment must be done by chest X ray or chest CT or chest MRI.
 - See Section 6.3.1 for further details
- Tumour assessment according to RECIST criteria (Ver1.1)
- Haematology, clinical chemistry analysis and sex hormone assessment

- For assessment of patient eligibility for study entry, the blood samples will be collected according to standard local practice and analysed at the local laboratory of each study centre using standard procedures. Platelets, AST, ALT, total bilirubin, E₂, and FSH must be measured. The actual values will not be collected in the eCRF or entered into the study database but confirmation that the values meet the inclusion or exclusion criteria will be recorded in the eCRF.
- Note that the E₂ and FSH assays used by the local laboratories may be different from those used by the central laboratory (Covance Asia Pte. Ltd., see Section 6.3.3).
- Histological or cytological confirmation of breast cancer
- Confirmation of ER, PgR and HER2 status of primary or secondary tumour tissue
- Confirmation that Patients fulfil all inclusion and exclusion criteria before randomised to treatment.
- Confirmation of AEs and concomitant medications

6.3 Efficacy

6.3.1 Progression Free Survival

Screening assessments should be performed within 21 days prior to randomisation and do not need to be repeated unless there is a reason to believe that there has been a change to tumour burden. However, tests performed before screening (within 6 weeks before randomisation) may be used as screening assessments at the discretion of the investigator(s) (with patient informed consent), although it is strongly recommended that tests are done within 3 weeks before randomisation where possible. For patients who have had prior first line chemotherapy for advanced breast cancer the screening imaging tests must have been performed at least 4 weeks after the last cycle of prior chemotherapy.

The screening assessment will be documented according to RECIST as the “baseline” assessment against which all subsequent tumour evaluations will be evaluated.

Tumour assessment will be done according to RECIST (Ver.1.1), which requires that the same method of assessment and the same technique should be used to characterise each identified and reported lesion at baseline and during follow up. Any other sites at which new disease is suspected should also be appropriately imaged. Imaging will be done by the investigator(s) or designee.

Any patient who discontinues treatment for reasons other than disease progression (except for withdrawal of consent) should continue, where possible, to have objective tumour assessments until week 24 or until objective progression is confirmed according to RECIST (Ver1.1) which is sooner.

6.3.2 Objective tumour response

Objective tumour response will be assessed at each tumour assessment until Week 24 in those patients with measurable disease at screening (see Table 2 for the timing of assessments).

Imaging methods for tumour assessment are provided in Section 6.3.1. Response will be evaluated using RECIST criteria (Ver.1.1), which are provided in Appendix D.

6.3.3 Oestradiol and follicle stimulating hormone serum concentration

Blood samples for measurement of E₂ and FSH serum concentrations will be collected from all patients at scheduled visits (see Table 2) by the investigator(s) or designee according to standard procedures. From Week 12 onwards, the blood samples will be drawn prior to ZOLADEX administration. See Section 6.2.1 for details of samples collected at screening.

All blood samples for E₂ and FSH serum concentrations analysis collected from Day 1 onwards will be analysed using a central laboratory according to the standard procedures described in the laboratory manual. The central laboratory will be required to provide up-to-date reference ranges.

See Section 7.1 for the total estimated volume of blood samples to be collected and the handling of blood samples. Evaluation of E₂ and FSH serum concentrations will be done by the central laboratory according to internal assay validation documentation.

Blood samples collection, transfer and storage for measurement of E₂ and FSH serum concentrations will be performed by .

PK subgroup

In addition, blood samples for measurement of additional E₂ samples will be collected from the patients in the PK subgroup, at the time points shown in Table 1, by the investigator(s) or designee according to standard procedures. On Day 1, blood samples are taken within 5 minutes of the protocol-specified time; on Days 2 and 3, sampling is done within 2 hours of the scheduled time; and from Week 4 onwards sampling is done within 7 calendar days of the scheduled time. From Week 12 onwards, the blood samples will be drawn before ZOLADEX 10.8 mg administration. The time that each blood sample is taken will be recorded in the eCRF.

6.4 Safety

The Principal Investigator is responsible for ensuring that all staff involved in the study are familiar with the content of this section.

6.4.1 Definition of adverse events

An adverse event is the development of an undesirable medical condition or the deterioration of a pre-existing medical condition following or during exposure to a pharmaceutical product, whether or not considered causally related to the product. An undesirable medical condition

can be symptoms (eg, nausea, chest pain), signs (eg, tachycardia, enlarged liver) or the abnormal results of an investigation (eg, laboratory findings, electrocardiogram). In clinical studies, an AE can include an undesirable medical condition occurring at any time, including run-in or washout periods, even if no study treatment has been administered.

Any deterioration of the disease targeted in the study and associated symptoms should not be regarded as an adverse event as far as the deterioration can be anticipated.

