1.4 Benefit/risk and ethical assessment

In women, ZOLADEX suppresses serum E₂ concentrations, which for 4-weekly ZOLADEX 3.6 mg administration is associated with a response in hormone-dependent breast cancer. The 12-weekly ZOLADEX 10.8 mg offers a potentially more convenient (less frequent) therapy to patients with breast cancer. Current data indicate little clinical difference of serum E₂ suppression between the 2 formulations in pre-menopausal breast cancer in trial 0004.

Generally, ZOLADEX 3.6 mg is well-tolerated in patients with breast cancer with the most frequent AEs being those commonly associated with serum E₂ suppression. Initially, breast cancer patients given ZOLADEX 3.6 mg may experience a temporary increase of serum E₂, signs and symptoms, which can be managed symptomatically. The most frequent AEs caused by ZOLADEX 10.8 mg is commonly associated with serum E₂ suppression and they can be managed symptomatically .

This study has a favourable risk/benefit assessment.

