5.8 Discontinuation of study treatment

Specific reasons for study completion are:

- Patient complete all treatment for 24 weeks and all assessments as scheduled
- Voluntary discontinuation by the patient who is, at any time, free to discontinue her participation in the study, without prejudice to further treatment
- Patient lost to follow-up
- Patients complete all of required assessment after meeting criterion of discontinuation

Specific reasons for discontinuing a patient from this study treatment are:

- Voluntary discontinuation by the patient who is, at any time, free to discontinue her participation in the study, without prejudice to further treatment
- Safety reasons, as judged by the investigator(s) and/or Study Delivery Team Physician
- Severe non-compliance to protocol, as judged by the investigator(s) and/or Study Delivery Team Physician
- Incorrect enrolment of the patient (ie, the patient does not meet the required inclusion/exclusion criteria) if this is considered to be a safety issue by the investigator(s) and Study Delivery Team Physician
- Pregnancy
- Observation of disease progression as defined by any one of the following:
 - Progression disease according to RECIST (Ver1.1) (See Appendix D.)
 - Death of the patient in the absence of progression

Any clinical evidence of disease progression (eg, worsening of symptoms such as bone pain) must be confirmed by imaging. Study treatment should only be stopped if clinical evidence of disease progression is confirmed by imaging.

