Disease progression can be considered as a worsening of a subject's condition attributable to the disease for which the investigational product is being studied. It may be an increase in the severity of the disease under study and/or increases in the symptoms of the disease. Events, which are unequivocally due to disease progression, should not be reported as an AE during the study.

Recurrence

Any events that are unequivocally due to recurrence of the breast cancer must not be reported as an AE (see Section 6.4.1).

Deaths

All deaths that occur during the study, or within the protocol-defined follow-up period after the administration of the last dose of study treatment, must be reported as follows:

- Death that is clearly the result of disease progression should be reported to the study monitor at the next monitoring visit and should be documented in the eCRF but should not be reported as a SAE
- Where death is not due (or not clearly due) to progression of disease under study, the AE causing the death must be reported to the study monitor as a SAE within 24 hours. The report should contain a comment regarding the co-involvement of progression of disease, if appropriate, and should assign main and contributory causes of death

- Deaths with an unknown cause should always be reported as a SAE. A post mortem may be helpful in the assessment of the cause of death, and if performed a copy of the post mortem results should be forwarded to the sponsor within the usual timeframes

A statement of death form should be submitted at any point during the study (to the sponsor) when a patient has died.

New cancers

The development of a new cancer should be regarded as an AE and will generally meet at least one of the seriousness criteria. New cancers are those that are not the primary reason for the administration of the study treatment and have been identified after the inclusion of the patient into the study. They do not include metastases of the original cancer. Symptoms of metastasis or the metastasis itself should not be reported as an AE/SAE as they are considered to be disease progression.

Overdose

Should an overdose (accidental or deliberate) occur, it must be reported in accordance with the procedures described in Section 13.2 regardless of whether the overdose was associated with any symptom or not. All symptoms associated with the overdose should be reported as AEs.

Pregnancy

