13.2 Overdose

- An overdose with associated AEs is recorded as the AE diagnosis/symptoms on the relevant AE modules in the eCRF and on the Overdose eCRF module.
- An overdose without associated symptoms is only reported on the Overdose eCRF module.

There is limited experience of ZOLADEX overdose in humans. In cases where ZOLADEX has unintentionally been re-administered early or given at a higher dose, no clinically relevant adverse effects have been seen. Animal tests suggest that no effect other than the intended therapeutic effects on sex hormone concentrations and on the reproductive tract will be evident with higher doses of ZOLADEX. If overdose occurs, this should be managed symptomatically.

Theoretically, overdosage of tamoxifen in humans might cause enhancement of the pharmacological side effects associated with its usage (eg, hot flushes, vaginal bleeding,

vaginal discharge, pruritus vulvae and tumour flare). There have been reports in the literature that tamoxifen given at several times the standard dose may be associated with prolongation of the QT interval of the electrocardiogram. Observations in animals show that extreme overdosage (100 to 200 times the recommended daily dose) may produce oestrogenic effects. There is no specific antidote to overdosage with tamoxifen and treatment must be symptomatic.

In this study, the following constitutes an overdose of study medication:

- >40 mg of tamoxifen in a one day period
- >1 ZOLADEX 3.6 mg injection in a 3-week period, or
- >1 ZOLADEX 10.8 mg injection in an 11-week period

Use of study medication in doses in excess of that specified above should not be recorded in the eCRF as an AE of 'Overdose' unless there are associated symptoms or signs.

An overdose with associated SAEs should be recorded as the SAE diagnosis/symptoms on the relevant SAE forms in the eCRF. Investigators must inform the sponsor of any SAEs within 24 hours of being aware of the SAE (see Section 6.4.4 for reporting of SAEs).

An overdose with associated non-serious AEs should be recorded as the AE diagnosis/symptoms on the relevant AE forms in the eCRF. In addition, the overdose should be reported on a separate clinical study overdose report form, which will be sent to the sponsor.

An overdose without associated symptoms should not be recorded as an AE in the eCRF. The overdose should be reported on a separate clinical study overdose report form, which will be sent to the sponsor.

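### Section 6.4.1 excludes any anticipated worsening of the cancer from AEs, while Sections 6.4.3 and 11.2.1 exclude only unequivocal progression, so drug-induced worsening can be missed or recorded inconsistently

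*Protocol*

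**What the plan says.** The protocol has two tests for when worsening of the breast cancer stays out of the adverse event record.

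- **Section 6.4.1 (definition).** After defining an AE broadly, including deterioration of a pre-existing condition, it carves out worsening of the target disease: such deterioration and "associated symptoms should not be regarded as an adverse event as far as the deterioration can be anticipated". The criterion is whether the worsening was foreseeable. Its cause plays no part.
- **Section 6.4.3 (recording).** Under the disease progression heading: "Events, which are unequivocally due to disease progression, should not be reported as an AE during the study". The same threshold is applied there to laboratory deterioration and to recurrence. The recurrence paragraph refers the reader back to Section 6.4.1.
- **Section 11.2.1.** It repeats the narrower threshold, as judged by the investigator.

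The protocol also foresees early drug effects. Section 1.4 says that initially "breast cancer patients given ZOLADEX 3.6 mg may experience a temporary increase of serum E₂, signs and symptoms". Section 13.2 gives tamoxifen's pharmacological side effects, in the setting of overdose, as a list that ends with "vaginal discharge, pruritus vulvae and tumour flare".

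**The concern.** An exclusion based on foreseeability cannot separate worsening caused by the disease from worsening caused by the treatment. A temporary increase in tumour symptoms after the first depot and the first tamoxifen tablets would be foreseeable precisely because it is a known drug effect. On the literal wording of Section 6.4.1, that makes it a candidate for exclusion. Under Section 6.4.3 it would be recorded.

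The safety comparison of the two formulations is a secondary objective and rests on AEs (Section 2.2). An event excluded at the definition never reaches the causality question that Section 6.4.3 asks for each ZOLADEX strength and for tamoxifen. It is then absent from the overall and drug-related AE tables in Section 12.2.2.1. If it was serious, it may also miss expedited reporting.

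**Working it through.** The plan attaches no figure to this point, so the check sets the provisions side by side.

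**1. Apply both tests to one case.** Take a patient with a temporary increase in tumour signs or symptoms soon after starting study medication, with no evidence of progression.

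| Provision | Question asked | Answer | Result |
|---|---|---|---|
| Section 6.4.1 | Is this anticipated deterioration of the disease or its symptoms? | Can be read as yes, given Sections 1.4 and 13.2 | Not an AE |
| Section 6.4.3, disease progression | Is it unequivocally due to progression? | No | Recorded as an AE |
| Section 11.2.1 | Does the investigator judge it unequivocally due to progression? | No | Recorded as an AE |

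The same patient gets opposite answers.

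**2. Does the narrower rule clearly prevail?** It does not.
- Section 6.4.1 is the definition and comes first. The collection rule in Section 6.4.3 covers all AEs that are reported, elicited or observed. Something that is not an AE under the definition falls outside it.
- Section 6.4.2 defines an SAE as an AE that meets a seriousness criterion, and Section 6.4.4 reports SAEs. Both inherit whatever Section 6.4.1 removes.
- Section 6.4.3 cites Section 6.4.1 as if the two tests were one. It does not say which governs when they differ.
- Section 6.4.3 describes progression loosely: "It may be an increase in the severity of the disease under study and/or increases in the symptoms of the disease". That gives a site little help in separating progression from a drug effect that shows as symptoms.

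**3. Can the number of affected events be computed?** The number left out would be 216 × r × q. Here 216 is the planned number of patients, all of whom take tamoxifen with one of the two ZOLADEX regimens. The rate of drug-induced worsening is r, and q is the share of such events that sites leave out. The documents give neither r nor q, so no count follows.

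**4. Which arms are exposed?** Both. Tamoxifen 20 mg daily is common to the arms, every patient starts ZOLADEX, and the exclusion is worded identically for all. Two design features could make site judgement uneven: the trial is open label (Section 3.2), and the 3.6 mg arm has dosing contacts at Weeks 4 and 8 that the 10.8 mg arm lacks (Section 5.5.2.1). The documents contain nothing that shows the direction or size of such an effect.

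**The case against.** The strongest reply is that the day-to-day recording rules are the narrow ones. A transient symptom attributed to a drug is not unequivocally progression, so a site working from Section 6.4.3 would record it. The cross-reference to Section 6.4.1 suggests that the authors meant a single rule. The protocol also treats these effects as drug effects: Section 13.2 calls flare a pharmacological side effect, and Section 1.4 puts the early "signs and symptoms, which can be managed symptomatically" in its tolerability paragraph. On that view they are not deterioration of the disease at all.

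Much of this stands. A reader might infer that tumour flare will go unrecorded and that its count will be near zero in each arm. The documents do not support that, because the narrower rules point the other way. What remains is that the definition comes first, has no exception for drug-induced worsening, and is not made subordinate to the later sections.

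Three other inferences are tempting and also fail.
- *A contradiction with Section 5.8.* That section says "Any clinical evidence of disease progression (eg, worsening of symptoms such as bone pain) must be confirmed by imaging", but it governs stopping treatment. AE recording may reasonably use a different standard of evidence.
- *A hidden difference between the two depots.* Tumour flare is named only for tamoxifen, which both arms take, and only in the overdose section. The early signs and symptoms in Section 1.4 are stated for 3.6 mg only and are not called flare.
- *A patient count.* Any incidence would have to come from outside the documents.

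Two facts limit the harm. Safety is not formally tested (Section 12.2), and deaths not clearly due to progression must still be reported as SAEs (Section 6.4.3).

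**Conclusion.** The concern holds as an inconsistency between the AE definition and the AE recording rules. Drug-induced worsening that the protocol itself anticipates can be left out, or recorded by some sites and not by others, and if serious may not be reported as an SAE. The likely consequence is under-ascertainment in both arms of an open-label trial with a descriptive AE comparison. A bias between arms is possible through uneven site judgement, but it is not shown. The size cannot be stated from the documents.

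The conclusion assumes that the early signs and symptoms in Section 1.4, or tumour flare in Section 13.2, can present to a site as worsening of the cancer or its symptoms. The protocol does not spell this out, though the wording allows it. The primary outcome, which rests on RECIST progression and death, is not touched by this point.

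**What to change.** - In Section 6.4.1, replace the sentence that excludes anticipated deterioration with the test already used in Sections 6.4.3 and 11.2.1: only events unequivocally due to disease progression or recurrence are not AEs.
- Add one sentence: a temporary worsening of tumour signs or symptoms that may be due to study medication is recorded as an AE, and as an SAE if a seriousness criterion is met.
- Carry the same wording into the eCRF instructions so that all sites apply one rule.

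The exclusion need not be restricted to progression confirmed by imaging. Scheduled tumour assessments fall only at Weeks 12 and 24, with others as clinically indicated, so that restriction could turn many ordinary disease symptoms into AEs.

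The cost is two sentences in an amendment and an update to the eCRF instructions. The small downside is some additional AE records of disease symptoms. The change affects recording only and leaves treatment as it is.
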